13 STATISTICAL CONSIDERATIONS

13.1 Sample size and power

In a preclinical prostate cancer model, xentuzumab suppressed IGF-1R phosphorylation (pIGF-1R) with an effect size of 0.68 (G*Power v3.1). Using Wilcoxon signed rank test, matched pairs, 2-tailed), recruitment of 20 patients (20 matched pre/post-treatment pairs) will be significant with 80% power, alpha = 0.05. Using a one-tailed test based on the hypothesis that xentuzumab will reduce pIGF-1R, we will need 16 patients, 16 matched pairs of tissue. We will recruit 20-30 patients in case some prostate biopsies are inadequate or unsuitable for translational studies.

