14 STATISTICAL ANALYSIS PLAN

Change in phospho-AKT (or downstream target) and phospho-IGF-1R immunoreactive score before and after treatment will be assessed using the Wilcoxon matched pairs signed rank test. Changes in PSA and other IHC markers including Ki67 index, IGF-1R, RRM2, CD31 and immune markers CD4, CD8, PD-L1, FoxP3 will be assessed using a paired samples t-test or a Wilcoxon matched pairs signed rank test if normality assumptions are not satisfied.

The severity of adverse events (AE) will be graded using the National Cancer Institute Common Terminology Criteria for Adverse Events (NCI CTCAE) version 5.0. Adverse events will be summarised; highest grade per patient AE summaries will be presented, according to whether the AEs are considered treatment-related or not, and over time.

A detailed statistical analysis plan will be written and will be finalised before any analysis is undertaken. The analysis plan will be written in accordance with current Standard Operating Procedures.

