Sample size calculations were repeated in October 2022 based on newly acquired preclinical data quantifying the amount of IGF axis pathway inhibition achieved by xentuzumab. This equates to the WINGMEN trial primary endpoint: the amount of IGF axis pathway inhibition. In a preclinical prostate cancer model, xentuzumab suppressed IGF-1R phosphorylation (pIGF-1R) with an effect size of 0.68 (G\*Power v3.1). Using Wilcoxon signed rank test (matched pairs, 2-tailed), recruitment of 20 patients (20 matched pre/post-treatment pairs) will be significant at the 5% level with 80% power. Using a one-tailed test, based on the hypothesis that xentuzumab will reduce pIGF-1R, we will need 16 patients (16 matched pairs of tissue). Therefore, we aimed to recruit 20-30 patients in case some prostate biopsies are inadequate or unsuitable for translational studies.

	n	Median serum IGF-1 nmol/l		n	Median serum IGF-1 nmol/l	p value
Benign epithelium						
IGF-1R score ≤ 10	77	16.54	IGF-1R score > 10	60	16.68	p=0.871
Malignant epithelium						
IGF-1R score ≤ 14	79	15.58	IGF-1R score > 14	60	17.07	p=0.038

**Table 2. Serum IGF-1 associates with IGF-1R immunoreactive score in malignant prostate epithelium.** Immunoreactive scores (calculated as described in [3] were divided by the median values. IGF-1R scores were generally higher in malignant epithelium, consistent with our earlier report of IGF-1R overexpression in prostate cancer [4], hence cut point of 14 in malignant epithelium vs 10 in benign epithelium. NB Two samples had no benign epithelium in the scored sections ([name], [name], [name], unpublished).

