## 4 STATISTICAL PRINCIPLES

### 4.1 Statistical Significance and Multiple Testing

*If the analysis is under a conventional (statistical hypothesis testing approach), state the level of statistical significance and the confidence intervals to be reported. Acknowledgement of the issue of multiple testing (if applicable), together with the rationale of the intention to formally or informally adjust for multiplicity. If no adjustment planned this will be stated. State which outcomes will be adjusted for multiplicity (if applicable).*

Initial analysis will assess variables for normal distribution using the Shapiro-Wilk test. All tests will be 2-tailed and  $p \leq 0.05$  will be accepted as statistically significant.

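### The 16-pair sample size assumes a one-tailed test, but the SAP makes every test two-tailed; 16 pairs then give about 70% power, and recruiting 20 leaves almost no allowance for unusable biopsies

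*SAP*

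**What the plan says.** SAP 3.2 reports a calculation repeated in October 2022. Its input is a preclinical prostate cancer model in which "xentuzumab suppressed IGF-1R phosphorylation (pIGF-1R) with an effect size of 0.68". Two sample sizes follow, one after the other.

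- Two-tailed: "Using Wilcoxon signed rank test (matched pairs, 2-tailed), recruitment of 20 patients (20 matched pre/post-treatment pairs"). The criterion attached to this number is a 5% significance level and power of 80%.
- One-tailed: "Using a one-tailed test, based on the hypothesis that xentuzumab will reduce pIGF-1R, we will need 16 patients (16 matched pairs of tissue"). Alpha and power are not restated here.

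The section then concludes that the aim was to recruit 20–30 patients, to cover biopsies that prove inadequate or unsuitable.

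Protocol 13.1 has the same pair of figures. The two-tailed one "will be significant with 80% power, alpha = 0.05", and then: "Using a one-tailed test based on the hypothesis that xentuzumab will reduce pIGF-1R, we will need 16 patients, 16 matched pairs of tissue".

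On the analysis itself, SAP 4.1 begins "All tests will be 2-tailed and" and goes on to accept p ≤ 0.05 as significant. SAP 4.1.1 makes the paired t-test the first choice for the primary endpoint, with the Wilcoxon test if the paired differences are not normally distributed. Protocol 14 says the change in "immunoreactive score before and after treatment will be assessed using the Wilcoxon matched pairs signed rank test" and does not mention sidedness. Neither document says that the primary analysis will be one-tailed.

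**The concern.** A one-tailed test at 5% uses the same critical value as a two-tailed test at 10%. The 16-pair figure is therefore sized at twice the two-sided error rate that SAP 4.1 allows. It stands beside the 20-pair figure with nothing to mark it as illustrative or inapplicable.

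Two things are at stake.

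- **The power claim.** If the trial ends with 16 to 18 usable pairs, the sample-size text would let a report describe it as adequately sized, when the planned test would be short of 80% power. That matters most if the result is null.
- **The attrition allowance.** The 20–30 range is justified as cover for poor biopsies. At the lower limit of 20, that is true only if some number well below 20 is enough. Under the two-tailed rule it is not. Losses are expected: Protocol 5.1 and SAP 6.2 list five ways in which a patient can become non-evaluable, and the estimand table in SAP section 2 excludes patients without scorable paired tissue and does not impute.

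**Working it through.** **Inputs.** Effect size 0.68 (SAP 3.2, Protocol 13.1), taken as the mean paired difference divided by the SD of the differences. Alpha 0.05 and power 80% (same sections), carried over to the one-tailed sentence, which does not restate them. Normally distributed differences (assumption).

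**Formula.** For n pairs, let N = n for the paired t-test, and N = n × 3/π = 0.955n for the Wilcoxon test (its asymptotic relative efficiency under normality). Power is the probability that a noncentral t variable with N − 1 degrees of freedom and noncentrality 0.68 × √N passes the critical value of central t at 1 − α (one-sided) or 1 − α/2 (two-sided).

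**Step 1: reproduce the plan's figures (Wilcoxon).**

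- 16 pairs, one-sided 0.05: N = 15.28, noncentrality 0.68 × √15.28 = 2.658, critical value 1.759, power 0.812. With 15 pairs it is 0.787, so 16 is the smallest number that reaches 80%.
- 20 pairs, two-sided 0.05: N = 19.10, noncentrality 2.972, critical value 2.100, power 0.803. With 19 pairs it is 0.780, so 20 is the smallest.

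Both stated figures are reproduced. Simulating the exact signed rank test (200,000 trials) gives 0.805 and 0.804.

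**Step 2: 16 pairs under the planned rule, two-sided 0.05.**

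- Wilcoxon: the noncentrality stays at 2.658 and the critical value rises to 2.141; power 0.697 (exact test, simulated: 0.683).
- Paired t: noncentrality 0.68 × √16 = 2.720, critical value 2.131; power 0.720.

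The shortfall from 0.80 is 8 to 12 percentage points.

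**Step 3: two-sided power at other evaluable numbers.**

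| Evaluable pairs | Wilcoxon | Paired t |
|---|---|---|
| 16 | 0.697 | 0.720 |
| 17 | 0.727 | 0.749 |
| 18 | 0.755 | 0.776 |
| 19 | 0.780 | 0.800 |
| 20 | 0.803 | 0.822 |

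So 80% power at 0.68 needs 20 pairs with Wilcoxon or 19 with the paired t-test.

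**Step 4: attrition allowance.**

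- 20 recruited: 20 − 20 = 0 pairs can be lost (Wilcoxon), or 20 − 19 = 1 (paired t).
- 30 recruited: 30 − 20 = 10, or 30 − 19 = 11.
- If 16 were a valid minimum, 20 recruited would allow 20 − 16 = 4 losses.

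The documents give no attrition rate. Purely as an illustration, four lost pairs out of 20 recruited would leave the power in Step 2.

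**Step 5: sensitivity to the distribution.** Other Wilcoxon efficiencies change the power at 16 pairs, two-sided: 0.647 at the minimum efficiency of 0.864, 0.764 for logistic differences and 0.890 for Laplace differences. None of these reproduces the plan's numbers: the one- and two-sided sizes would be 18 and 22, 14 and 18, and 10 and 13. Of the variants tried, only the normal case gives 16 and 20, so it is the fair basis for comparison.

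**The case against.** The strongest reply is that nothing has been miscalculated. Both figures are right for the test that each names, the 16-pair sentence is openly conditional on a one-tailed test, and the two-tailed figure that governs stands immediately before it. The sentence introducing the 20–30 range follows both calculations, and its lower limit equals the two-tailed requirement. SAP 3.2 also gives 24 pairs at a more cautious effect size of 0.6 and a supporting check with 25 patients. Protocol 2 and SAP 6.2 speak of 30 patients, which would leave ample margin. The SAP is dated June 2024 and records that recruitment was complete by Q1 2023, so a correction cannot change enrolment.

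All of that stands, and it limits the point. It does not make 16 pairs applicable to a two-tailed analysis, and it does not supply an allowance for losses at the lower limit of 20.

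Two stronger readings are tempting but are not supported.

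- A reader might infer that a two-sided p between 0.05 and 0.10 could be called a success on a one-tailed reading. SAP 4.1 rules that out for every test. Protocol 14 is silent on sidedness but defers to a detailed plan finalised before any analysis, and Protocol 14.4 and SAP 1 require deviations to be described and justified. A one-tailed claim would be a declared departure from the plan. It is not an open option.
- A reader might infer that 20 pairs is the only size in the documents that supports 80% power. The paired t-test reaches it at 19 pairs, and the 24-pair calculation uses a different effect size.

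**Conclusion.** The point holds as an internal inconsistency. The 16-pair figure does not apply to the planned analysis: at effect size 0.68, 16 pairs give two-sided power of about 0.68–0.70 (Wilcoxon) or 0.72 (paired t). The two-tailed figure of 20 pairs is correct, so the design has a valid two-tailed basis. What fails is the implied cushion: recruiting 20 carries no allowance for unusable biopsies under Wilcoxon and one pair under the t-test.

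The practical weight is modest. The significance rule is already fixed and recruitment is over, and whether the shortfall is real depends on the number of evaluable pairs, which the documents do not give. The figures assume that 0.68 is a paired standardised effect, that the one-tailed calculation used alpha 0.05 and 80% power, and that the differences are normal. The exact reproduction of 16 and 20 supports all three.

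**What to change.** In SAP 3.2, and in Protocol 13.1 if it is amended:

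1. Delete the one-tailed 16-patient sentence, or mark it as not applicable because SAP 4.1 fixes a two-sided 5% test.
2. Give the two-sided power at effect size 0.68 for 16 to 20 evaluable pairs, for both the Wilcoxon test and the paired t-test, as in the Step 3 table.
3. State that 80% power at 0.68 needs 20 evaluable pairs (Wilcoxon) or 19 (paired t), and that 20 recruited therefore carries essentially no attrition allowance. Limit the statement to that effect size, so that it does not conflict with the 24-pair calculation at 0.6.

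The cost is a few sentences and a small table, with no new patients, data or analyses. The downside for the sponsor is that the stated power becomes less favourable at 16 to 18 pairs, and at 19 under Wilcoxon.

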### 3.3 Statistical Interim Analysis, Data Review and Stopping guidelines

*State if there is a Data and Safety Monitoring Committee referencing the trial DSMC Charter (OCTRU GEN-011) for full details, but include the planned timing of meetings and of any formal comparative interim analysis. The latter should be outlined in the protocol and should be included here either in full, or summarised here with cross-reference to the full details in a separate document such as the DSMC\_Report\_Template (OCTRU Template OST-005, OCTRU SOP STATS-004 Interim Analysis).*

*If no DSMC is reviewing accruing data, state this together with justification.*

The roles of the Trial Steering Committee and DSMC will be fulfilled by the Independent Early Phase Trial Oversight Committee (IEPTOC). The IEPTOC (at least 3 members including an independent chair) will provide overall supervision of the safe and effective conduct of the study according to its terms of reference. At least annually it will review study progress against agreed milestones, adherence to protocol, patient safety and consider new information. The IEPTOC has the authority to recommend study closure where appropriate.

### 3.4 Timing of Final Analysis

*Provide details of the final analysis time-points – clarifying if the outcomes will all be assessed at the same time or are there different time-points for analysis, for example short term and long-term outcomes, or dose escalation and dose expansion phase.*

To assess feasibility of tissue processing, two trial cases identified by [name], Consultant Prostate Pathologist, will be selected to check the tissue analysis pipeline. Sections of formalin-fixed paraffin-embedded (FFPE) diagnostic (PRE) and in theatre (POST) biopsy cores will be cut for primary endpoint immunohistochemistry (IHC) (2 sections), multiplex immunofluorescence (mIF, 1 section), RNA extraction (3 sections) and up to 4 additional sections depending on tumour content of diagnostic biopsies, which must not be cut to exhaustion.

Outcomes will be assessed at different time points as follows:

#### 3.4.1 Primary endpoint

The primary endpoint, the amount of IGF axis pathway inhibition, will be assessed by batch analysis using automated IHC for phospho-IGF-1R and downstream marker phospho-S6. Multiple rounds of validation have confirmed that the selected antibodies are stable, providing reproducible signal in multiple prostate samples and analytical runs. Analysis of freshly cut paired sections of diagnostic biopsy and in-theatre prostate biopsy cores from a non-trial subject confirmed that the selected phospho-epitopes are stable between these two time-points. The paired diagnostic (PRE-treatment) and in theatre (POST-treatment) biopsy cores of the two trial patients identified above will be analysed in the same staining run, alongside a negative IHC control. If the results are satisfactory, sections will be cut from the remaining PRE/POST biopsy core pairs and freshly stained for phospho-IGF-1R and phospho-S6. Again, each pair of tissues will be analysed in the same staining run, alongside a negative control.

#### 3.4.2 Secondary endpoints

Feasibility of recruitment and safety data will be accrued in real time, the latter during trial treatment and up to and including the End of Study visit. These data will be analysed after data lock.

#### 3.4.3 Research/tertiary endpoints

There are several tertiary and exploratory endpoints for which data will be collected in this trial.

- IGF-1, IGFBP3, insulin and PSA levels will be collected on a per patient basis in real time and analysed after data lock.
- Serum IGF bioactivity will be batch analysed by phospho-IGF-1R ELISA after data lock, ensuring pairs of PRE/POST serum samples from individual subjects are analysed in the same batch.
- For metabolomics profiling, samples of sodium heparin plasma will be molecular weight filtered then transferred on ice to the [name] laboratory in a single batch on completion of recruitment. Pairs of PRE/POST plasma will be analysed by mass spectrometry in the same analytical run.
- PBMC immunophenotyping will be done by mass cytometry (CyTOF) using 36 markers of diverse immune cell classes and their functional states. We will use non-trial samples to test the viability of cryopreserved cells post-thawing and to determine the number PBMC cells required for acquisition to identify low frequency but functionally important immune subsets. Pairs of PRE/POST PBMCs from individual subjects will be barcoded with a CD45 based approach, allowing all samples to be batch analysed in a single run. This significantly reduced batch effects).

- ctDNA: currently there are no funds to sequence these samples. Opportunities will be explored to perform this analysis in collaboration, for example using a next generation sequencing assay that identifies prostate-cancer relevant genomic alterations as in [5].
- Exploratory IHC markers (see WINGMEN\_DataDefinitions&Tables Section 5.2.1) will be batch analysed as for primary endpoint markers (Section 3.4.1 above) after completion of primary endpoint IHC.
- RNA will be extracted from unstained FFPE sections of diagnostic biopsy and in-theatre prostate biopsy cores, initially using freshly cut sections of the two first trial patients identified in Section 3.4, for transcriptional profiling. RNA will be stored in a designated -80°C freezer. If RNA yield and quality are sufficient for sequencing, RNA will be extracted from FFPE sections of the remaining cases and stored at -80°C as above. If RNA yield is insufficient, we will re-review each biopsy with [name] to decide whether we can cut additional sections from some/all of the cases. RNA will be sent on dry ice to Azenta for quality control and sequencing as described in WINGMEN\_DataDefinitions&Tables Section 5.2.2. Final analysis will be performed when RNA-seq data have been accrued from all evaluable trial subjects (i.e. those with sufficient tumour in the diagnostic biopsy to allow within patient comparison with RNA extracted from prostate cancer cores post-xentuzumab).
- Mutation panel screening and TPMRSS2-ERG FISH will be performed on sections of radical prostatectomies as single batches after the samples from the last patient have been collected.
- Phospho-proteomic profiling: fresh frozen punch biopsies taken from unfixed prostatectomies are stored in the Oxford Radcliffe Biobank. Given that we have no matched pre-treatment fresh frozen biopsies, we plan to hold analysis of these samples until the other endpoint analyses have been completed. If sufficient funds remain, and if we can access fresh biopsies from Gleason-matched prostatectomies in non-trial patients, we will analyse tumour lysates by Reverse Phase Protein Array (e.g. Institute of Genetics and Cancer in Edinburgh: [www.ed.ac.uk/cancer-centre/facilities/htpu-microarray-services/reverse-phase-protein-arrays](http://www.ed.ac.uk/cancer-centre/facilities/htpu-microarray-services/reverse-phase-protein-arrays)). The analysis will be performed in a single batch after samples from the last patient have been collected.

#### 3.4.4 Final integration of translational research data

Final data integration will be performed when all results have been obtained from the primary, secondary and research/tertiary endpoint markers, as described in WINGMEN\_DataDefinitions&Tables Section 5.3. Set-up of a private cBioPortal will allow us to study associations and correlations between different data types. Exploratory analyses will be conducted using the cBioPortal and followed up using independent analyses where relevant. Recruitment was completed by Q1 2023 and the study is funded until April 2025 to allow time for analysis of these datasets.

#### 3.5 Blinded analysis

There will be no blinding for treatment: all trial subjects will be treated with xentuzumab. Research staff of the Translational Histopathology Lab will be blinded. [name] lab members will not be blinded as to whether the samples are PRE or POST xentuzumab.

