#### 4.1.1 Primary endpoint analysis

PRE/POST FFPE tissue biopsy sections stained for phospho-IGF-1R and phospho-S6 will be scanned and analysed on the HALO platform. This is a deep-learning convolutional neural network that generates H-Scores, representing the sum of the % tissues staining 0 (negative), 1+, 2+ and 3+ to generate a score range of 0-300. If the staining intensity is not sufficient to define a scoring range for H-Scores, percentage of positively stained cells will be used as output instead. To assess the significance of differences before and after xentuzumab, the PRE/POST HALO scores will be analysed using a paired t-test, or, if the paired differences do not follow a normal distribution, the Wilcoxon matched pairs signed rank test. Phospho-IGF-1R staining patterns will also be assessed by [name], to semi-quantitatively score signal in the plasma membrane, cytoplasm and nucleus. Existing data from our group suggest that nuclear IGF-1R associates with higher stage prostate cancer [3] .

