### 5.6.3 Research/tertiary endpoints

Tertiary endpoints will be assessed in the [name] lab, Translational Histopathology Lab, the [name] Research Chemistry lab, and the Azenta Sequencing Facility using tested, standardised protocols.

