#### 5.6.3.1 Tissue endpoints

The reliability of research/tertiary IHC (e.g. Ki67, IGF-1R, RRM2, CD31) and TMPRSS2-ERG FISH will be checked by including positive and negative controls in each staining run. The signal will be quantified using HALO (WINGMEN\_DataDefinitions&Tables Sections 4.3.1, 5.2.1 and 5.2.3) and reviewed with trial pathologist [name] to check: staining of controls (e.g. cell pellets as shown in WINGMEN\_DataDefinitions&Tables Figure 1A), technical quality of tissue staining, and whether pathological appearances are accurately represented by the HALO data.

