## 6 ANALYSIS

*Statistical methods to be used to compare groups for primary and secondary outcomes and methods for point and interval estimation. Include methods for additional analyses, such as adjusted analyses and subgroup analyses, together with which populations will be analysed.*

**Note:** *It may be appropriate to list the outcome definitions, analysis methods, missing data and sensitivity analyses separately for each primary and secondary outcome to be analysed.*

Section 4 above describes the methods that will be used to assess statistical significance of differences in endpoint marker signal between samples taken pre- and post- xentuzumab.

The primary endpoint will be assessed by HALO analysis of 2 immunohistochemical (IHC) markers: phospho-IGF-1R and phospho-S6 (see WINGMEN\_DataDefinitions&Tables Figure 1 and Appendix 2). The scanned IHC images will be quantified using HALO by DPhil student [name] ([name] lab), and HALO data

will be reviewed with trial pathologist [name] as described in Section 5.6 above. Depending on the results of this assessment, we may use mean percentage change in one or both markers to quantify the amount of IGF axis inhibition. This measure will be used in correlation analyses with research/tertiary endpoints in both the entire population and in pre-defined subgroups as described in WINGMEN\_DataDefinitions&Tables Section 5.3 and 5.3.1.

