### 6.3 Sensitivity Analysis

*Describe any analysis utilised to check the robustness of the results. This may include repeating the primary analysis for different patient populations. Any sensitivity analyses checking the robustness of the results against the missing data assumptions should be included here or in the missing data section.*

Primary endpoint analysis of phospho-IGF-1R and phospho-AKT or S6 IHC will be performed in parallel with controls as in WINGMEN\_DataDefinitions&Tables Figure 1 and will require 2x 4 µm FFPE sections. [name] advises that it is usually possible to cut maximum ~24 4-5 µm sections from a prostate biopsy, so the majority of trial subjects will have additional material if there are technical issues with initial analysis. Method optimisation indicates that IHC is capable of detecting changes in phospho-S6 phosphorylation comparable to changes detected on western blot of parallel whole cell extracts (see in WINGMEN\_DataDefinitions&Tables Figure 1)

Similarly, the planned blood sample collection will provide sufficient serum and sodium heparin plasma to repeat assays for IGF bioactivity and metabolomic profiling if there are technical issues with initial assays. Both assays on circulating biomarkers will use controls in the form of recombinant IGF-1 and metabolite controls respectively. The lower detection limit for phospho-IGF-1R ELISA is 2 nmol/l IGF-1 equivalents, with approximately linear detection up to 20 nmol/l (WINGMEN\_DataDefinitions&Tables Figure 3).

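### The primary HALO scores appear to come from a lab that knows PRE from POST, and no visible text requires scoring on coded images in this single-arm trial

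*SAP*

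**What the plan says.** - **Who is blinded.** SAP 3.5 blinds the research staff of the Translational Histopathology Lab. Of one other laboratory, whose name is redacted, it says that its "lab members will not be blinded as to whether the samples are PRE or POST xentuzumab".
- **Who scores the primary endpoint.** SAP 6: "The scanned IHC images will be quantified using HALO by DPhil student", followed by a redacted name and a redacted laboratory. The HALO data are then reviewed with the trial pathologist, with a pointer to SAP 5.6. The visible text does not say whether that review is blinded.
- **What the review covers.** SAP 5.6.3.1, written for the tertiary tissue markers, includes a check of "whether pathological appearances are accurately represented by the HALO data".
- **What depends on it.** SAP 6 adds: "Depending on the results of this assessment, we may use mean percentage change in one or both markers" to quantify the amount of inhibition.
- **Safeguards.** SAP 4.1.1 says of HALO: "This is a deep-learning convolutional neural network that generates H-Scores". SAP 3.4.1 says that "each pair of tissues will be analysed in the same staining run, alongside a negative control".
- **Repeats.** SAP 6.3 expects that most participants "will have additional material if there are technical issues with initial analysis".
- **Design.** SAP 2 and 3.1 describe a trial without a control arm in which each patient is his own control.

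**The concern.** The primary result is the POST score compared with the PRE score in the same man. No concurrent untreated pairs exist to absorb a measurement artefact. If slides from one time point are handled even slightly differently in scoring, the paired test counts the difference as pathway inhibition. A scorer who knows the time point also knows the direction the hypothesis predicts, because Protocol 13.1 and SAP 3.2 both state that phospho-IGF-1R is expected to fall.

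The plan already blinds one laboratory. On the visible text, that blinding does not reach the step where the primary numbers are produced.

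**Working it through.** **1. Is the scorer in the unblinded laboratory?** SAP 3.5 contrasts two groups: the Translational Histopathology Lab (blinded) and one name-redacted laboratory (not blinded). SAP 6 places the scorer in a name-redacted laboratory. SAP 5.6.3 reads "Tertiary endpoints will be assessed in the [name] lab, Translational Histopathology Lab" and then lists the chemistry laboratory and the sequencing facility separately. The redacted laboratory that stands beside the Histopathology Lab is therefore probably the one in both 3.5 and 6. This is likely but cannot be proved from the text. If the laboratories differ, the only visible blinding statement still covers Histopathology Lab staff alone, and the scorer is not placed there.

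**2. Does any other visible text close the gap?**
- Protocol 6.2 labels research samples with the date taken, which can reveal the time point.
- SAP 7 has an independent statistician repeat the analyses. Re-scoring of images is not mentioned.
- No visible passage requires coded images, HALO settings fixed in advance, or a blinded second read.

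**3. Which decisions do the safeguards leave open?** Same-run staining controls staining variation, and automation controls how a given image is scored. The visible text does not require any of the following to be settled without knowledge of time point: region selection, algorithm settings, slide acceptance, repeats, the choice of H-score or percent positive, and the pathologist's review.

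**4. The plan's own sample size.** Inputs from Protocol 13.1 and SAP 3.2: standardised paired effect 0.68, Wilcoxon signed-rank, 80% power, alpha 0.05. The method is noncentral t with n multiplied by the Wilcoxon efficiency 3/π = 0.955.
- Two-sided, n = 20: effective n = 20 × 0.955 = 19.1, noncentrality 0.68 × √19.1 = 2.97, power 0.803.
- One-sided, n = 16: power 0.812.

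Both stated sizes reproduce, and blinded scoring would not change them.

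**5. What a scoring shift would do.** The documents give no estimate of scorer bias, so the shift δ is an assumption, in SD units of the paired differences. With no true drug effect, the paired t statistic is noncentral t with n − 1 degrees of freedom and noncentrality δ√n. The false-positive rate is the probability that it exceeds the two-sided 5% limits. Example: n = 20, δ = 0.2 gives noncentrality 0.2 × √20 = 0.894 and a rate of 13.6%. The Wilcoxon rates come from simulation (exact test, normal differences, 20,000 replicates). The SAP rule (Shapiro-Wilk, then t or Wilcoxon) was simulated with 4,000 replicates.

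| Assumed shift δ | δ / 0.68 | Wilcoxon, n = 20 | Paired t, n = 20 | SAP rule, n = 20 | Wilcoxon, n = 30 | Paired t, n = 30 |
|---|---|---|---|---|---|---|
| 0 | 0% | 4.8% | 5.0% | not run | 5.1% | 5.0% |
| 0.1 | 15% | 6.7% | 7.1% | 7.1% | 8.1% | 8.3% |
| 0.2 | 29% | 12.9% | 13.6% | 12.9% | 18.1% | 18.5% |
| 0.3 | 44% | 23.6% | 24.7% | 25.0% | 33.9% | 35.5% |
| 0.5 | 74% | 54.8% | 56.5% | 57.0% | 73.6% | 75.4% |

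A separate run of the n = 20 Wilcoxon simulation gave 7.2, 12.9, 23.9 and 54.6% for the four non-zero shifts. The choice of test hardly matters. More pairs make the problem worse, because a fixed bias is detected more reliably. Thirty pairs is an upper bound, since recruitment of 20 to 30 allows for inadequate biopsies.

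**The case against.** The strongest counter-arguments are these.

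- **The link rests on redacted names.** Several redacted groups appear in the SAP. This stands, and it is why the point says only that the scores appear to come from the unblinded laboratory.
- **A companion document was not available.** SAP 1 calls Data Definitions and Tables integral to the SAP, and SAP 6 and 6.2 refer to it for the primary endpoint. It could contain image coding or fixed HALO settings. This stands too. If it does, the sponsor should cite it and reconcile it with SAP 3.5, which states non-blinding outright.
- **The scoring is automated, and some of the listed decisions are not described.** No visible text says that the operator selects regions or tunes settings slide by slide, and SAP 5.6.1 says the Histopathology Lab optimised the markers. Settings fixed once for all slides would not separate PRE from POST, and the same holds for one H-score or percent-positive choice applied throughout. This lowers the expected bias. It does not show that the choices are made blind, and settings chosen after seeing results by time point can still favour one answer.
- **The one-or-both-markers choice is largely separate.** It affects the percentage-change measure that SAP 6 uses in correlation analyses, not the PRE/POST tests of SAP 4.1.1. The pathologist's subcellular scoring is likewise supplementary. Both are correct, and neither carries the main point.
- **The bias sizes are assumed, and this is a Phase 0 mechanism study.** Both are true. The table shows sensitivity and is not evidence that this trial's scores are biased.

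**Conclusion.** The concern holds as a risk of detection bias in the primary endpoint. It is not proof that the results are biased. SAP 3.5 explicitly leaves one laboratory unblinded, SAP 6 probably puts the primary scoring in that laboratory, and no visible text requires coded images. Without a control arm, nothing in the analysis can separate a scoring shift from a drug effect.

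The size is unknown. A shift of 0.1 SD has little consequence (about 7% instead of 5% with 20 pairs). A shift of 0.2 SD, 29% of the planned effect, more than doubles the error rate. A shift of 0.5 SD is an extreme case that automated scoring makes less likely. Confidence is medium, because of the redacted laboratory names and the unavailable companion document. The point should be fixed, mainly because the remedy is cheap.

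**What to change.** Amend SAP 3.5 and 6 as follows.

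1. Keep each PRE/POST pair in the same staining run. Those who stain may hold the pairing.
2. After scanning, release the images to the HALO operator and the reviewing pathologist under random codes, with no sampling date visible. The trial office holds the PRE/POST key.
3. On the coded images, complete and lock:
   - region selection and HALO settings;
   - the H-score or percent-positive choice, one per marker for all slides;
   - slide exclusions and repeats, with reasons;
   - the pathologist's review and the supplementary subcellular scoring.
4. Fix whether the percentage-change measure uses one or both markers before the key is released.
5. Release the key only after the lock.
6. State in the report whether the reviewing pathologist also selected the blocks.

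If the companion document already provides coding or fixed settings, cite it in SAP 3.5 and remove the contradiction.

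**Cost.** Relabelled image files, a key held by the trial office, SAP wording and a short delay before results can be seen by time point. No extra tissue or assay is needed. One limit remains: tissue appearance, or the pathologist's part in block selection (Protocol 6.1), may reveal the time point. Blinding of the review may then be incomplete unless another pathologist reads the images, which would add cost.
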